8.0 CLINICAL MANAGEMENT ISSUES

8.1 Toxicity

General instructions for management of Grades 1-4 AEs is provided in [section 8.1](#). Refer to sections [8.2](#), [8.3](#), and [8.4](#) for information on the following specific toxicities:

- Rifamycin Hypersensitivity Syndrome (RHS)
- Suspected allergic reactions to dolutegravir

- **Cutaneous**
- **Drug-associated fever**
- **Elevated liver-associated enzymes**
- **Peripheral neuropathy**
- **Suicidal ideation**

8.1.1 Grade 1 or 2

Participants who develop a Grade 1 or 2 AE or toxicity may continue all study-supplied drugs (INH, RPT and DTG if receiving through the study) at the discretion of the site investigator, and will be followed carefully.

If the site investigator or participant chooses to discontinue any study-supplied drug, the site should notify the A5372 core team within 72 hours (preferably within 48 hours). The premature treatment/study discontinuation evaluations must be completed, and then the participant will be taken off study.

8.1.2 Grade 3 or 4

For Grade 3 or 4 AE or toxicity that is definitely, probably, or possibly related to study-supplied drugs, study-supplied drugs **as well as any other drugs suspected in the site investigator's causality assessment** must be permanently discontinued and participants followed carefully. Premature treatment discontinuation evaluations should be performed. In the event of Grade 3 or 4 toxicities, the A5372 core team should be notified within 72 hours (preferably within 48 hours).

The participant should be followed until the AE has decreased to Grade ≤ 2 . After the AE has decreased to Grade ≤ 2 , the premature study discontinuation evaluations must be completed, and then the participant will be taken off study.

8.2 Rifamycin Hypersensitivity Syndrome (RHS)

Participants who develop signs or symptoms suggestive of RHS (i.e., fever, myalgia, rash, hypotension, clinical hepatitis) should undergo clinical evaluation and laboratory testing including comprehensive metabolic panel, CBC with manual differential, and other tests that, at the discretion of the site investigator, are necessary to exclude likely alternative diagnoses (e.g., if symptoms suggest influenza, a nasopharyngeal aspirate for viral testing could be sent). Any participant in whom the investigator suspects RHS and no alternative etiology is identified must permanently discontinue INH, RPT, and other study-provided medications. Premature treatment discontinuation evaluations should be completed. The participant should be followed until the AE has decreased to Grade ≤ 2 . After the AE has decreased to Grade ≤ 2 , premature study discontinuation evaluations should be completed, and then the participant will be taken off study.

8.3 Suspected Allergic Reactions to Dolutegravir

Participants with Grade ≥ 3 allergic reactions, which are considered possibly or probably

related to DTG should be evaluated by the investigator and must discontinue study-provided DTG and other study-provided medications. Locally provided DTG must be stopped as well. Premature treatment discontinuation evaluations should be completed. The participant should be followed until the AE has decreased to Grade ≤ 2 . After the AE has decreased to Grade ≤ 2 , premature study discontinuation evaluations should be completed, and then the participant will be taken off study. ART management will be at the discretion of the site investigator.

8.4 Other Toxicities

Cutaneous

Participants with an isolated Grade 1 or Grade 2 rash may continue study-supplied drugs at the study investigator's discretion. Participants should be advised to contact the site staff immediately if there is any worsening of the rash, if any systemic signs or symptoms worsen, or if mucosal involvement develops.

If Grade ≥ 3 , all study-provided drugs must be discontinued, **as well as any other drugs suspected in the site investigator's causality assessment**. Premature treatment discontinuation evaluations should be completed. The participant should be followed until the AE has decreased to Grade ≤ 2 . After the AE has decreased to Grade ≤ 2 , premature study discontinuation evaluations should be completed, and then the participant will be taken off study. ART management will be at the discretion of the site investigator.

Drug-Associated Fever

If Grade ≥ 3 , all study-supplied drugs must be discontinued, **as well as any other drugs suspected in the site investigator's causality assessment**. Premature treatment discontinuation evaluations should be completed. The participant should be followed until the AE has decreased to Grade ≤ 2 . After the AE has decreased to Grade ≤ 2 , premature study discontinuation evaluations should be completed, and then the participant will be taken off study.

Elevated Liver-Associated Enzymes

Sites must notify the core team within 72 hours and hold study-supplied drugs (INH, RPT, and DTG if applicable) if any of the following criteria are met.

- a) Grade 3 or 4 AST, ALT or total bilirubin values are recorded;
- b) ALT $\geq 3 \times \text{ULN}$ and bilirubin $\geq 2 \times \text{ULN}$ ($> 35\%$ direct bilirubin);
- c) ALT $\geq 3 \times \text{ULN}$ with symptoms (new or worsening) believed to be related to liver injury or hypersensitivity

For any Grade 1 AST (SGOT), ALT (SGPT) (1.25 to $< 2.5 \times \text{ULN}$) or total bilirubin (1.1 to $< 1.6 \times \text{ULN}$) elevation, repeat liver chemistries (ALT, AST, total bilirubin) should be conducted at regular intervals at the investigator's discretion until resolution to $\leq \text{ULN}$ **or to baseline if abnormal at entry**.

For Grade 2 AST (SGOT), ALT (SGPT) (2.5 to $5 \times \text{ULN}$), or total bilirubin (1.6 to $< 2.6 \times \text{ULN}$) increase, study-supplied drugs will be held until the levels return to Grade ≤ 1 , and then liver

chemistries repeated until resolution to <ULN or to baseline if abnormal at entry, as above. Reintroduce the study-supplied drug(s) with caution. **Locally provided DTG should be discontinued if suspected in the site investigator's causality assessment.**

INH, RPT, and study-supplied DTG will be permanently discontinued in the event of Grade 3 to 4 AST (SGOT), ALT (SGPT) (≥ 5 ULN) or total bilirubin ($\geq 2.6 \times$ ULN) toxicity that is definitely, probably, or possibly related to study-supplied drugs. **Locally provided DTG should be discontinued if suspected in the site investigator's causality assessment.** Premature treatment discontinuation evaluations should be completed. The participant should be followed until the AE has decreased to Grade ≤ 2 . After the AE has decreased to Grade ≤ 2 , premature study discontinuation evaluations should be completed, and then the participant will be taken off study. ART management will be at the discretion of the site investigator.

In consultation with the team, careful assessments should be done to rule out the use of alcohol, non-study medication-related toxicity, or viral hepatitis (including viral hepatitis complicated by immune reconstitution inflammatory syndrome) as the cause for any liver toxicity that warrants permanent study drug discontinuation based on the liver stopping criteria specified above. Specific tests that may be considered are listed on the PSWP.

Peripheral Neuropathy

Peripheral neuropathy associated with INH is usually avoided by the concurrent administration of pyridoxine (vitamin B6). In this study, all participants will take vitamin B6 concomitantly with INH. If peripheral neuropathy develops, every effort should be made to determine the etiology (i.e., whether the neuropathy is due to INH toxicity, alcohol, or other factors). Participants with peripheral neuropathy Grade ≤ 2 may be entered into the study, but should be monitored carefully for any progression of peripheral neuropathy.

For Grade 1 or 2, continue study-supplied drugs and follow the participant more frequently for progression of peripheral neuropathy. Consider increase in vitamin B6 dose.

For Grade 3 or 4, study-supplied drugs must be permanently discontinued, **as well as any other drugs suspected in the site investigator's causality assessment.**

Premature treatment discontinuation evaluations should be completed. The participant should be followed until the AE has decreased to Grade ≤ 2 . After the AE has decreased to Grade ≤ 2 , premature study discontinuation evaluations should be completed, and then the participant will be taken off study.

Suicidal Ideation

Participants will be monitored appropriately and observed for suicidal ideation and behavior or any other unusual changes in behavior. It is recommended that the investigator consider mental health consultation or referral for participants who experience signs of suicidal ideation or behavior. For Grade 3 or 4 suicidal ideation, study-supplied drugs must be permanently discontinued, **as well as any other drugs suspected in the site investigator's causality assessment.** Locally provided DTG

must be stopped as well. Premature treatment discontinuation evaluations should be completed. The participant should be followed until the AE has decreased to Grade ≤2. After the AE has decreased to Grade ≤2, premature study discontinuation evaluations should be completed, and then the participant will be taken off study.

Other toxicity

Toxicity management will be performed per the standard clinical practice.

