6.3.7 Laboratory Evaluations

At screening and entry all laboratory values must be recorded on the eCRF. For post-entry assessments, record abnormal laboratory findings as per [section 7.2](#).

Hematology

Hemoglobin, hematocrit, red blood cells, white blood cell count, absolute neutrophil count (ANC), and platelets.

Liver Function Tests (LFTs)

Total bilirubin, AST (SGOT), ALT (SGPT).

Blood Chemistries

Sodium, potassium, creatinine, and albumin.

Pregnancy Testing

For women with reproductive potential: Serum or urine β -HCG. Urine test must have a sensitivity of 15-25 mIU/mL.

In addition to a pregnancy test at the Screening visit within 30 days prior to entry, negative pregnancy will be confirmed within 48 hours prior to Entry. **A pregnancy test will be performed and a negative result available** prior to Screening X-ray.

NOTE: If screening visit occurs within 48 hours prior to entry, only one test will occur.

Record pregnancy and pregnancy outcome per [section 8.5](#).

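### Protocol 8.4: a related Grade 2 liver event meeting criterion (b) or (c), without suspected RHS, has cautious reintroduction as its only written follow-on, and the term for liver stopping criteria is left undefined

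*Protocol*

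**What the plan says.** Under elevated liver enzymes, Protocol 8.4 gives one instruction for three criteria. Sites notify the core team within 72 hours and "hold study-supplied drugs (INH, RPT, and DTG if applicable) if any of the following criteria are met". The criteria are (a) a Grade 3 or 4 AST, ALT or total bilirubin; (b) ALT ≥3x ULN with bilirubin ≥2x ULN and more than 35% direct; and (c) ALT ≥3x ULN with new or worsening symptoms attributed to liver injury or hypersensitivity.

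The later paragraphs set the follow-on by grade:

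- Grade 2 (AST or ALT 2.5 to 5x ULN, or total bilirubin 1.6 to <2.6x ULN): "study-supplied drugs will be held until the levels return to Grade" 1 or lower, chemistries are repeated, and then "Reintroduce the study-supplied drug(s) with caution".
- Grade 3 or 4 (AST or ALT from 5x, or bilirubin from 2.6x ULN): "INH, RPT, and study-supplied DTG will be permanently discontinued in the event of Grade 3 to 4 AST (SGOT), ALT (SGPT" or bilirubin, provided the event is at least possibly related to study-supplied drugs.

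A further paragraph asks for a causality work-up of any "liver toxicity that warrants permanent study drug discontinuation based on the liver stopping criteria specified above". It does not say which criteria those are.

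**The concern.** Criteria (b) and (c) are named alongside Grade 3 or 4 values as reasons to hold drug and alert the core team, yet neither is given an outcome of its own. When the values lie in the Grade 2 band, the grade rule takes over, and its only written next step is to restart.

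At stake is re-exposure to INH, RPT and, in Arm 1, study-supplied DTG after a drug-related combined ALT and bilirubin rise, or after symptomatic liver injury. The regimen is preventive. Sites could also handle identical cases differently and each be compliant, because the reference to stopping criteria can be read with or without (b) and (c).

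**Working it through.** No sample size or error rate is involved. The check applies the limits printed in 8.4 to test cases and reads off the action.

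**Can (b) and (c) be met wholly within Grade 2?**

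- ALT: the criterion starts at 3x and Grade 2 starts at 2.5x, so the overlap starts at max(3, 2.5) = 3x. It ends below 5x, where the permanent-stop rule begins.
- Bilirubin for (b): max(2, 1.6) = 2x, ending below 2.6x.
- For (c): ALT 3x to <5x with symptoms, bilirubin below 2.6x, and no Grade 3 AST or symptom.

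So yes, both can.

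**Test cases** (multiples of ULN; AST below Grade 3; event related; RHS not suspected)

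| ALT | Bilirubin | Other | Grade | Criterion met | Written action in 8.4 |
|---|---|---|---|---|---|
| 4 | 2.3 | 50% direct | 2 | (b) | Hold, then reintroduce |
| 4 | 1.0 | symptoms below Grade 3 | 2 | (c) | Hold, then reintroduce |
| 5.5 | 1.0 | none | 3 | (a) | Permanent stop |
| 2.7 | 1.0 | none | 2 | none | Hold, then reintroduce |

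The first, second and fourth rows end in the same place. Any ALT ≥3x is already at least Grade 2 and so already held. Within the Grade 2 band, (b) and (c) therefore add only the 72-hour notice.

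**State at restart.** The hold ends at Grade 1 or lower, which by the printed limits means ALT <2.5x and bilirubin <1.6x ULN. Entry (4.1.9) required ALT <2.5x and total bilirubin ≤1.5x ULN, so a value meeting (b) or (c) is above what was allowed at eligibility. Section 5.2 allows 42 days for a 28-day course, 42 − 28 = 14 days of slack, so resuming after a short hold is feasible.

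**Other routes to a stop**

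- 8.2: mandatory if RHS is suspected and no other cause is found. Clinical hepatitis is among its listed signs, so it takes some (c) cases.
- 8.1.2 and 8.3: mandatory for a related Grade 3 or 4 event, or a Grade 3 or higher allergic reaction attributed to DTG. Neither applies in the Grade 2 band.
- 8.1.1 and 9.1: a stop is permitted at the investigator's choice.
- 7.4: the core team may act to protect a participant.

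After these, (b), and (c) without suspected RHS, have no mandatory stop when the event is related and Grade 2.

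**The reference to stopping criteria.** If it includes (b) and (c), it sits awkwardly with the Grade 2 restart sentence, which makes no exception for them. If it does not, nothing requires a stop. Either way the sentence orders a work-up, not a discontinuation.

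**Direct bilirubin.** The 6.3.7 liver panel is "Total bilirubin, AST (SGOT), ALT (SGPT"), and 8.4 describes "repeat liver chemistries (ALT, AST, total bilirubin) should be conducted at regular intervals". Neither names the direct fraction that (b) uses.

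**The case against.** The strongest defence is that 8.4 is coherent as it stands. One list triggers an immediate hold and a call to the core team; grade and causality then settle what follows. Even (a) is a permanent stop only if the event is at least possibly related. Everyone meeting (b) or (c) is off study-supplied drug at once, the core team hears within 72 hours, and the investigator may stop at any point. The list (a) to (c) is also the only one in that subsection introduced as criteria, so the later reference may well be meant to include all three, with a specific combined or symptomatic criterion qualifying the general Grade 2 rule.

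Much of this stands. The immediate protection is complete, and the shared list sets only the hold and the notice. A reader might infer that the protocol treats (b) and (c) as equal to Grade 3 or 4 for all purposes, that it keeps dosing such participants, or that it forces a rechallenge. The text supports none of these. What survives is that the printed follow-on for these cases is restart, that stopping rests on individual judgement, and that the phrase which might say otherwise is undefined.

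A reader might also infer that (b) cannot be applied because direct bilirubin is not in the listed panels. That goes too far. The criterion names the fraction, so a site applying it would obtain it. In this band the fraction now changes only the notice, since the hold applies anyway. On further work-up, 8.4 says "Specific tests that may be considered are listed on the PSWP"; neither that list nor the contents of the 8.2 metabolic panel was available to check.

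**Conclusion.** The point holds in limited form. For a related Grade 2 event that meets (b), or meets (c) without suspected RHS, 8.4 writes down hold and cautious reintroduction and nothing further, and leaves it unclear whether these criteria count as stopping criteria. This is a cheap improvement to participant safety and to consistency between sites, not a failure of immediate protection.

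Its size cannot be stated. The documents give no rate for these events and none is assumed. The conclusion rests on the grade limits printed in 8.4; the DAIDS grading table itself was not available.

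**What to change.** In Protocol 8.4:

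1. Directly after the reintroduction sentence, add that it does not apply when (b) or (c) is met and the event is at least possibly related to study-supplied drugs. INH, RPT and study-supplied DTG are then permanently discontinued, as for related Grade 3 or 4 values. Section 8.2 continues to govern suspected RHS.
2. Define the liver stopping criteria as related Grade 3 or 4 values plus related (b) or (c).

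As a consequential clarification, name direct bilirubin in 6.3.7 and 8.4 as a reflex test when ALT is ≥3x and total bilirubin is ≥2x ULN, because under change 1 the fraction would decide a permanent stop.

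The cost is two sentences and one reflex test. The halt rule in 10.5.1 and AE collection are unchanged. The downside is some additional permanent discontinuations, expected to be few although the documents give no rate. Each arm enrolls 36 to obtain 32 evaluable, 36 − 32 = 4 spare, and 10.4 replaces participants who drop out between sampling times.

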6.2.3 Post-Entry Evaluations

On-Treatment Evaluations

Day 3

A study visit including sparse PK sampling will occur on Day 3 with a window of ± 2 days.

Day 14

A study visit including sparse plasma PK sampling will occur on Day 14, with a window of ± 2 days.

Day 21

A study visit including sparse plasma PK sampling will occur on Day 21, with a window of ± 2 days.

PK sampling at Day 3, Day 14, and Day 21 may only occur after ensuring 3 days of consecutive dosing of ART and/or RPT/INH prior to study visit. This will be recorded per participant self report.

Day 28

A study visit including intensive PK sampling will occur on Day 28 (window -2/+14 days).

PK sampling at Day 28 may only occur after ensuring 3 days of consecutive dosing of ART and RPT/INH prior to study visit (participant self report is sufficient).

NOTE: Participants will have 6 weeks to complete 4 weeks of on-study treatment.

Day 42

A follow up study visit should occur approximately 14 days following the completion of study treatment. The window for the day 42 follow-up visit is -2/+14 days.

NOTE: The timing of the day 42 visit may vary for some participants as participants will have up to 6 weeks from enrollment to complete 4 weeks of treatment.

Event-Driven Evaluations**Day 49 Confirmation of Suspected Virologic Failure**

Participants with plasma HIV RNA > 50 copies/mL at the Day 42 follow-up visit will return for a confirmatory plasma HIV RNA measurement approximately 7 days after the original sample collection or as soon as testing results are available.

At non-US sites, an additional plasma sample will also be collected for possible resistance testing, if viremia is confirmed. At US sites, the confirmatory sample should be sent to reflex for resistance testing if HIV viremia is confirmed, where feasible. If not feasible, an additional plasma sample for resistance testing should be collected at time of confirmation of viremia. Resistance testing should include integrase and reverse transcriptase resistance.

The window for the day 49 confirmation of suspected virologic failure visit is +28 days.

NOTE: The timing of the day 49 visit may vary for some participants as participants have up to 6 weeks from the time of enrollment to complete 4 weeks of treatment.

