6.2.4 Discontinuation Evaluations

Evaluations for Participants Who Do Not Start Study Treatment

All eCRFs must be keyed for the period up to and including the entry visit.

Discontinuation Evaluations

If a confirmation of suspected virologic failure visit is not necessary (i.e., plasma HIV RNA is determined to be <50 copies/mL at Day 42), participants should discontinue study once they complete their Day 42 follow-up visit. Refer to the Discontinuation Log in the A5372 eCRF completion guideline.

If a confirmation of suspected virologic failure visit is necessary based on the Day 42 follow-up visit plasma HIV RNA, participants should discontinue study after they complete their Day 49 Confirmation of Suspected Virologic Failure visit. Refer to the Discontinuation Log in the A5372 eCRF completion guideline.

Premature Discontinuation Evaluations

Participants who prematurely discontinue the study will have evaluations performed as indicated in the schedule of evaluations and then be taken off study.

Participants who discontinue study participation due to Grade 3 or 4 toxicity attributed to study drug should have premature study discontinuation evaluations completed per the SOE when the toxicity has decreased to Grade ≤2 and then be taken off study. No further evaluations can be performed on a participant after study discontinuation. Refer to the Discontinuation Log in the A5372 eCRF completion guideline.

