9.2 Premature Study Discontinuation

- Request by the participant to withdraw
- Requirement for prohibited concomitant medications (see section [5.5](#))
- Clinical reasons believed life-threatening by the physician, even if not addressed in the [toxicity section](#) of the protocol
- Failure by the participant to complete either of the intensive PK visits
- Participant repeatedly noncompliant (per investigator's discretion) with study medications as prescribed
- Request of the primary care provider if she or he thinks the study is no longer in the best interest of the participant
- At the discretion of the ACTG, IRB/EC, FDA, NIAID, Office for Human Research Protections (OHRP), other government agencies as part of their duties, investigator, or industry supporter

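### Participants who stop study drugs early leave the study without a required post-treatment visit or a route to confirm viremia, although they count in the viral load outcome

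*Protocol*

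**What the plan says.** **Completers.** Protocol 6.2.3: "A follow up study visit should occur approximately 14 days following the completion of study treatment". This is Day 42, window -2/+14 days. A viral load above 50 copies/mL there brings the participant back for a confirmatory measurement. Plasma for resistance testing is tied to that confirmation visit (6.2.3, 6.3.13).

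**Early stoppers.**
- Grade 1-2 event with a study-supplied drug stopped by choice (8.1.1): "The premature treatment/study discontinuation evaluations must be completed, and then the participant will be taken off study". No resolution of the event is required.
- Related Grade 3-4 event (8.1.2 and most parts of 8.4; similarly 8.3 and 6.2.4): permanent stop, follow-up to Grade 2 or below, final evaluations, off study.
- Suspected rifamycin hypersensitivity with no other cause found (8.2): the participant "must permanently discontinue INH, RPT, and other study-provided medications", with the same exit at Grade 2 or below and no lower limit on the starting grade.
- Reasons for premature study discontinuation (9.2) include "Failure by the participant to complete either of the intensive PK visits".
- After exit (6.2.4): "No further evaluations can be performed on a participant after study discontinuation".

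**Liver events (8.4).** For Grade 1, "repeat liver chemistries (ALT, AST, total bilirubin) should be conducted at regular intervals at the investigator's discretion until resolution to" the upper limit of normal (ULN) or below, or baseline if abnormal at entry. For Grade 2, drugs are held to Grade 1 or below and tests are repeated to below ULN or baseline. For related Grade 3-4, "The participant should be followed until the AE has decreased to Grade" 2 or below, then off study.

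**Analysis.** The SAP's third secondary outcome (3.2) is the proportion above 50 copies/mL at Day 28 and/or Follow Up. It is reported for the Safety Analysis Population (4.9), which is defined by minimum doses taken and not by completion (4.2.3).

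**The concern.** The protocol treats stopping the drugs and leaving the study as nearly one event. The viral load outcome looks beyond the end of dosing and is reported on everyone dosed, but the visit that supplies its Follow Up part is assured only for those who finish. People who stop because of an adverse event are not a random subset, so their missing results cannot simply be assumed to resemble the others'.

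Two things are at stake. First, the virologic suppression result at Follow Up could describe mainly those who tolerated the combination. Second, viremia found at a premature visit has no stated confirmation or resistance-testing route, in a trial whose question is whether DTG exposure remains adequate. Late or unresolved adverse events in early stoppers also fall outside required observation. Under Protocol 7.3.4, once a participant is off study only suspected unexpected serious adverse reactions learned of passively are reported to DAIDS.

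**Working it through.** **1. The plan's calendar.** 28 + 14 = Day 42, and 4 + 2 = 6 weeks on study. With up to 6 weeks to complete treatment, 6 + 2 = 8 weeks. With up to 3 further weeks for confirmation, 8 + 3 = 11 weeks. All agree with Protocol 3.0. The 14-day post-treatment period is therefore a planned part of the design.

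**2. Each exit against that visit.**

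| Route | Condition for leaving | Minimum time after last dose |
|---|---|---|
| Completer (6.2.4) | Day 42 done, or Day 49 if viral load is above 50 | about 14 days |
| Grade 1-2 stop (8.1.1) | evaluations done | none |
| Related Grade 3-4 (8.1.2, 8.3, 8.4) | Grade 2 or below, evaluations done | none fixed |
| Suspected hypersensitivity (8.2) | Grade 2 or below, evaluations done | none fixed; a Grade 1-2 case meets the condition at the start |
| Missed intensive PK visit (9.2) | evaluations done | none |

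No section keeps any of the last four groups on study until about 14 days after the last dose. Pregnancy is handled separately: 8.5 encourages the participant to stay on study for outcome data but ends study evaluations.

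**3. Confirmation route.** 6.2.3 and 6.2.4 name only the Day 42 viral load as the trigger. 6.3.13 places resistance plasma at the confirmation visit. A value above 50 copies/mL at a premature visit triggers nothing in the text.

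**4. Analysis route.** SAP 4.2.3 keeps dosed early stoppers in the population. SAP 3.2, 4.1 and 4.9 do not say whether a viral load from a premature visit counts as Day 28 or Follow Up. They do not say how a participant with neither value is handled either. The missing-data text in SAP 4.8.2 covers PK only.

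**5. What the missing rule could do (illustration only).** Assume 36 dosed in an arm, k early stoppers with no usable viral load, and no viremia in the rest. k is an assumption; the documents give no rate. The exact 95% Clopper-Pearson interval (the SAP's method) for 0/n has upper limit 1 - 0.025^(1/n). For k/n the limits are the 2.5% point of Beta(k, n-k+1) and the 97.5% point of Beta(k+1, n-k).

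| k | Stoppers left out | Stoppers counted as above 50 copies/mL |
|---|---|---|
| 0 | 0/36: 0 to 9.7% | 0/36: 0 to 9.7% |
| 1 | 0/35: 0 to 10.0% | 1/36 = 2.8%: 0.1 to 14.5% |
| 2 | 0/34: 0 to 10.3% | 2/36 = 5.6%: 0.7 to 18.7% |
| 6 | 0/30: 0 to 11.6% | 6/36 = 16.7%: 6.4 to 32.8% |

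Leaving stoppers out barely moves the interval. Counting them as failures moves both the estimate and the interval. The plan does not choose.

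**6. Liver passages side by side.** On the protocol's own bands, Grade 2 means ALT or AST 2.5 to 5 x ULN and bilirubin 1.6 to below 2.6 x ULN. The Grade 3-4 rule ends follow-up anywhere at or below that range; the Grade 1 and Grade 2 rules run to ULN or baseline. A participant leaving under the Grade 3-4 rule could have ALT of 3 x ULN or more with bilirubin of 2 x ULN or more. With direct bilirubin above 35%, that still meets the section's own hold criterion (b). Also, 8.1.1 takes a Grade 1-2 stopper off study directly, while 8.4 has Grade 1-2 liver tests repeated to ULN or baseline.

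**The case against.** The strongest reply is that early stoppers are not left unobserved. The schedule (Table 6.1-1, footnote c) has evaluations at treatment stop and/or study stop, and Grade 3-4 cases have both. The rows of that table for viral load and liver tests are missing from the text available, so a reader who infers that viral load and event outcome are never seen goes beyond the documents. What stands is narrower: no observation after the end of treatment is required of those who stop.

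A reader might also infer that the worst liver injuries are followed least. That fails on time: the Grade 3-4 rule has no cap, and a slow case may be followed past Day 42. The rules also serve different situations, since Grade 1-2 participants may continue or restart study drugs and related Grade 3-4 participants may not. The Grade 1 repeats are at the investigator's discretion. Only the difference in stated end points is established.

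Nor are the adverse event proportions biased as defined. Protocol 10.2.2.1 and SAP 3.2 count events while DTG and 1HP are being given, so a lost later visit cannot change them.

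The gap between 36 enrolled and 32 evaluable does not measure early exit. It covers unusable PK measurements, and participants without the required samples are replaced (10.4). The trough reductions cited from the weekly rifapentine study in healthy volunteers concern another regimen and a very small group, and are not evidence for this one.

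Finally, few may stop: in the cited 3HP study in a similar population, all 60 who started completed (2.2). And 8.1.1 is a general rule that refers to later sections for specific toxicities, which softens its conflict with 8.4. Neither point supplies the missing visit or confirmation route.

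**Conclusion.** The point holds in limited form. Early stoppers can leave the study before the post-treatment visit, viremia found at a premature visit has no stated confirmation or resistance route, and these participants stay in the population for an outcome that includes Follow Up. The primary PK outcomes and the adverse event outcome as defined are untouched. The effect is confined to the Follow Up part of the viral load outcome and to the description of late or unresolved events. Its size cannot be stated without an early-stop rate; the table above shows only how sensitive the result would be for assumed numbers. The conclusion rests on the text of the sections cited and does not assume that the discontinuation evaluations lack a viral load. It is an inexpensive improvement, not a flaw that undermines the trial.

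Separately, the liver end points within 8.4 differ by grade, and 8.1.1 conflicts with 8.4. This review does not say which end point is right.

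**What to change.** 1. In Protocol 6.2.4, 8.1.1, 8.1.2, 8.2 to 8.4 and 9.2, separate treatment discontinuation from study discontinuation. Anyone who has taken 1HP stays on study, off treatment, through the existing follow-up visit, timed about 14 days from the last 1HP dose, unless consent is withdrawn. The existing rule for viral load above 50 copies/mL, with its confirmation visit and resistance sampling, applies to them too. Pregnancy remains under 8.5.
2. In 9.2, treat a missed intensive PK visit in a dosed participant as not PK-evaluable, not as an exit from the study. This fits the replacement rule in 10.4.
3. In SAP 4.9, state how a viral load from a premature visit and a missing viral load enter the Day 28 and/or Follow Up outcome.
4. The sponsor should reconcile the liver follow-up end points in 8.4, and 8.1.1 with 8.4. The choice of end point is the sponsor's.

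Cost: protocol and SAP wording, plus one already scheduled visit (and confirmation where triggered) for the participants who stop early. No new procedure is needed. The downside is some extra site follow-up.
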